## 1.0 Objectives

Tobacco use continues to be a leading cause of preventable disease and early death. The majority of people who smoke are interested in quitting and attempt to quit each year, but successfully quitting can be challenging for many reasons. In particular, smoking cessation can be especially hard when smokers are dealing with unmet social and health needs and areas of financial stress, which are disproportionately experienced by low-income smokers. In this study, we extend previous research showing that food insecurity is independently associated with higher odds of smoking and can act as a barrier to quitting smoking. Therefore, we design and test a 12-week intervention to assist food-insecure smokers who are ready and willing to make a quit attempt. Beyond providing the quit assistance that smokers normally receive, the research seeks to address food insecurity in the short-term by providing economic food assistance during the quit attempt that will help to meet food needs. We will adapt a patient navigation model in which a designated study navigator can help bridge resources and referrals related to tobacco cessation and food access, and provide economic food assistance based on individualized needs. We will recruit 60 participants for a 12-week study, and all participants will be smokers who are ready to quit and have recently experienced food insecurity. All participants will receive quit assistance and information on local food assistance resources, and a monthly check-in from the navigator. In addition, half of the participants (n=30) will be randomly assigned to the intervention arm, and will receive economic food assistance to partially meet their food needs and reduce food insecurity during the cessation attempt. We will assess feasibility and acceptability of the intervention, and preliminary outcomes related to smoking cessation, such as the number of quit attempts lasting 24 hours or more and the longest length of abstinence from tobacco. By conducting this study, we seek to understand whether this type of intervention is feasible to conduct, and acceptable to those who participate. The study findings will serve as the basis of future research on understanding and addressing tobacco-related and food insecurity-related health disparities. Our main research question is whether addressing food insecurity specifically during a smoking cessation attempt is helpful for increasing quitting success rates.

## 2.0 Background

### 2.1 Relevant Prior Experience and Gaps in Current Knowledge

In the U.S., the existence of socioeconomic disparities in tobacco use is a widely known public health problem. Of the numerous factors that account for socioeconomic disparities in smoking, one major reason is due to disparities in successful quitting. That is, regardless of socioeconomic background, the majority of smokers are interested in quitting (68%), and over half (55%) report making at least one 24-hour quit attempt in the past 12 months. However, there are disparities in rates of successful quitting by socioeconomic status. There is a need to consider novel strategies to address cessation disparities to mitigate the disproportionate burden of tobacco-related health problems in socioeconomically disadvantaged population groups.

### 2.2 Relevant Preliminary Data

There are many sources of socioeconomic stress that disproportionately affect populations with disadvantage. Food insecurity occurs when there is lack of access at all times to enough food for an active, healthy life. In 2019, 35% of households living below the federal poverty level (FPL) experienced food insecurity, compared to 5% of households above 185% of FPL. Food insecurity is also significantly higher among racial/ethnic minority households, female-headed households, and households with children. Food insecurity is an important social determinant of health that is independently predictive of a range of chronic disease outcomes, influencing health behaviors related to chronic diseases (such as medication adherence, diet quality, eating behaviors, and substance use). As such, food insecurity's effects on health behaviors are most widely considered within specific chronic diseases that are diet-sensitive (such as diabetes, hypertension, and hyperlipidemia), or are transmitted through risky behaviors especially among vulnerable populations (such as people living with HIV). Beyond behaviors within specific chronic diseases, food insecurity has also been linked with tobacco smoking behavior. Food insecurity is known to increase the odds of current smoking, independent of poverty and other socioeconomic indicators, as well as mental health characteristics that increase likelihood of smoking.

A growing body of research has suggested a bidirectional and mutually reinforcing relationship between food insecurity and tobacco use. Food insecurity is conceptualized to pose a unique barrier to quitting due to factors such as psychological stress from food insecurity and appetite regulation from nicotine. In turn, however, tobacco-related expenditures can compete with household spending (a phenomenon known as smoking-induced deprivation) to exacerbate food insecurity. While the body of research suggests that addressing food insecurity could enhance cessation outcomes, this has not been formally tested to our knowledge. That is, such findings on food insecurity and smoking cessation are drawn mainly through epidemiological studies following a nationally representative sample of smokers over time, or cross-sectional studies estimating the quit ratio (i.e., the proportion of former smokers among ever smokers). In order to examine food insecurity's potential effects on the cessation process and outcomes, and whether addressing food insecurity results in more favorable cessation outcomes, there is a need to conduct more rigorous clinical and intervention-based studies.

### 2.3 Scientific Rationale and Significance

This proposal is significant for smoking cessation research because there are relatively few evidence-based cessation interventions that seek to address the role of socioeconomic stress (such as food insecurity) to improve cessation outcomes. This proposal is also significant for food security research. With food insecurity's wide-ranging adverse impacts on chronic disease and health outcomes, food insecurity has been estimated to contribute \$77.5 billion annually in excess healthcare costs. The latest food security evidence review by Feeding America (the largest hunger relief organization in the U.S.) included smoking as a known factor that increases the risk of food insecurity. By addressing food insecurity as a potential strategy to promote successful quit attempts, this research

has implications for addressing the double burden of food insecurity and tobacco use. As one of the first interventions to examine whether addressing food insecurity affects cessation outcomes, this research provides innovative directions in tackling socioeconomic disparities in smoking.

### 3.0 Study Endpoints

As a pilot study, primary endpoints are feasibility and acceptability of the intervention. Secondary endpoints are the number of quit attempts lasting 24 hours or more over the past 3 months, and the longest length of smoking abstinence in days over the past 3 months.

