### 5.0 Procedures Involved

#### 5.1 Study Design (Overview)

For most participants, the full length of participation is about 2.5-3 hours spread across 13 weeks (intervention is 12 weeks, and an additional week is included as pre-intervention baseline). For a small proportion of participants (n=8-10) who agree to participate in an end-of-study qualitative interview to share their experiences of the study, the full length of participation is about 2.5-3.5 hours.

1. Telephone conversation to discuss study, assess interest and eligibility, answer participant questions, and provide instructions on consent process (30 minutes)
2. Receive consent form via mail. Prior to randomization, complete a baseline assessment via telephone/online survey (30-45 minutes)
3. At week 1 post-randomization, connect with study navigator by telephone to receive information and referrals about tobacco cessation and food assistance (30 minutes)
- 3a. Participants in the intervention arm will receive instructions about funds (5-10 minutes)
4. Week 4 post-randomization, check-in call with study navigator (10-15 minutes) 4a. Participants in the intervention arm receive additional funds (0-1 minute required for participant)
5. Week 8 post-randomization, check in call with study navigator (10-15 minutes)
- 5a. Participants in the intervention arm receive additional funds (0-1 minute required for participant)
6. Week 12 post-randomization, follow-up assessment (30-45 minutes)
7. Post-intervention qualitative interviews (30-45 minutes)

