**RANDOMIZATION, ALLOCATION:** After the baseline telephone (or online) survey is completed, participants will be randomized in the Intervention arm or the Control arm with a 50/50 chance to be randomized in either arm. The study analyst who has no contact with participants will use a computer-generated random number table to assign participants. In either arm, in Week 1 of the study, all participants will be connected to receive usual care for tobacco cessation, based on their preferences. In either arm, the study navigator (a community health worker) will review participant responses from the baseline telephone survey and reach out to all participants by telephone. This conversation may involve referrals to the tobacco quitline, referrals to counseling/classes offered at MetroHealth or in the community (such as Freedom from Smoking classes), nicotine replacement therapy and/or pharmacotherapy as prescribed by their primary care provider. The study navigator will provide linkages and information to the services available to the participant, which will be documented in a semi-structured call log, and used as the basis of following up on use of tobacco cessation services in subsequent telephone check-ins in Week 4 and Week 8.

In either arm, participants also receive information from the study navigator about local food assistance resources available to them, such as a list of food pantries and community meal sites and eligibility information about federal food assistance programs. Provision of this information will also be documented by a semi-structured call log, and will be used as the basis of following up on food assistance resources in subsequent check-ins in Week 4 and Week 8. Information about tobacco cessation and food assistance resources are provided by telephone and/or in writing, which is within the scope of work for a community health worker.

In the Intervention arm only, participants will receive economic food assistance to meet their individual food and grocery needs during the cessation attempt/study period. This is provided on a monthly basis (3 times during the 12 weeks of the study) during Week 1, Week 5, and Week 9.

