Participants in the Intervention arm will be provided \$83 per month (for a total of \$250 for the 12 weeks) to partially support the cost of food (i.e., provide short-term food insecurity relief) during the cessation attempt. These funds will be in the form of VISA gift cards, a check, a direct deposit transaction, or a Zelle transaction, depending on the participant's choosing. The check, direct deposit, and Zelle options are processed through PNC Bank's E-payment system. We are NOT collecting any bank information from the participants. The participant will confirm their bank account information with PNC to deposit the funds or mail the check, but the researchers will not see that information.

**Follow-ups:** About 4 weeks after randomization, the study navigator will conduct a general check-in call with all participants by telephone to follow-up on referrals provided and additional referrals needed. The length of the call is anticipated to be 15 minutes. The content/topics and length of discussions will be documented through call logs.

About 8 weeks after randomization, the study navigator will conduct a general check-in call with all participants by telephone to follow-up on referrals provided and additional referrals needed. The length of the call is anticipated to be 15 minutes. The content/topics and length of discussions will be documented through call logs.

Twelve weeks after randomization (end-of-study), the study coordinator will contact participants to complete the follow-up telephone or online REDCap survey, which is expected to last 30-45 minutes.

**END-OF-STUDY QUALITATIVE INTERVIEWS:** Participants who were randomized to the intervention group and have completed the protocol will be invited to participate in an end-of-study qualitative interview to provide more context about food access, and to share their experiences with the intervention.

**Recruitment:** Similar to the recruitment procedures for the overall study, we will first mail an invitation letter to prior participants, who can contact the research team if they are interested and willing to discuss their food access and study intervention experiences through a telephone interview. As needed, we will follow up with a telephone call to the target subsample of participants who were sent invitation letters.

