### 6.2 Inclusion and Exclusion Criteria

Inclusion:

- Aged 21 or older
- Current tobacco smoker, defined as having smoked daily over the past 7 days
- Willing to make a serious quit attempt in the next 30 days ("Yes" to "In the next 30 days, are you willing to try quitting smoking for at least 24 hours?")
- Considered food insecure, based on past 30-day screening using the 2-item Hunger Vital Sign, or by virtue of having visited a food pantry in the past 30 days
- A reliable telephone number and a local mailing address where participant can be reached during the duration of the study

Exclusion:

- Aged 20 or younger
- Non-smoker, or a current tobacco smoker who did not smoke daily over the past 7 days
- Not interested in quitting at this time, assessed by unwillingness to make a serious quit attempt in the next 30 days ("No" to "In the next 30 days, are you willing to try quitting smoking for at least 24 hours?")
- Did not recently experience food insecurity, based on past 30-day screening using the 2-item Hunger Vital Sign, or has not visited a food pantry in the past 30 days
- Does not have a reliable telephone number and a local mailing address where participant can be reached during the duration of the study

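### Both cessation endpoints use a three-month recall not tied to randomisation, while the survey falls 84 days after it with no completion window

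*Combined protocol and SAP*

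**What the plan says.** Section 3.0 names two secondary endpoints. One counts attempts: "the number of quit attempts lasting 24 hours or more over the past 3 months". The other, listed second, measures duration and is defined as "the longest length of smoking abstinence in days over the past 3 months". Neither mentions randomisation or any other start date. Section 1.0 lists the same two outcomes with no time window at all.

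Section 5.2 sets the survey date: "Twelve weeks after randomization (end-of-study), the study coordinator will contact participants". Neither that section nor Section 5.1 gives an earliest or latest completion date, or a rule for late surveys.

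Section 5.1 describes 13 weeks of participation: "intervention is 12 weeks, and an additional week is included as pre-intervention baseline". Section 5.2 places randomisation after the baseline survey: "After the baseline telephone (or online) survey is completed, participants will be randomized". No maximum interval from screening to randomisation is given.

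Section 6.2 requires daily smoking over the 7 days before screening and a yes to "In the next 30 days, are you willing to try quitting smoking for at least 24 hours".

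Section 11.0 plans t-tests and chi-square tests of group differences. It has no provision for a recall period that differs from the follow-up period.

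**The concern.** An outcome in a randomised comparison should count what happens after allocation. A recall counted back from the day of the survey does so only if its length equals the time since randomisation. Here the two lengths differ, and nothing holds the survey to a fixed day.

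Two errors can follow. If the survey is on time, the recall is longer than follow-up and can take in attempts that precede allocation. Participants are selected for willingness to try within 30 days of screening, so an attempt before randomisation is plausible. If the survey is late enough, the recall starts after randomisation. The first days of follow-up are then lost, and days beyond week 12 are counted instead. For longest abstinence, an early run can be cut short or missed.

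At stake are the preliminary cessation estimates that Section 11.0 sets out to obtain and that Section 1.0 says will inform later research. The primary endpoints, feasibility and acceptability, are not touched.

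**Working it through.** The plan states no figure to reproduce here. The check is calendar arithmetic.

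**Inputs**
- Recall length W: three calendar months (Section 3.0). Counted back from every date in a four-year calendar, this is 89 to 92 days, mean 91.3.
- Survey day S: 84 + L, where 84 = 12 × 7 (Section 5.2) and L is the number of days late.
- Screening-to-randomisation gap g: not stated, so shown over a range (assumption).
- Daily smoking in the 7 days before screening (Section 6.2), which makes a 24-hour attempt in those days very unlikely.

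**Formulas**
- Pre-randomisation days inside the recall = max(0, W − S).
- Early post-randomisation days lost = max(0, S − W).
- Pre-randomisation days that also fall after screening, for an on-time survey = min(W − 84, g).

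**Survey on time (L = 0).** The overhang is 89 − 84 = 5 to 92 − 84 = 8 days. At W = 91 it is 7 days, or 7/91 = 7.7% of the recall (range 5/89 = 5.6% to 8/92 = 8.7%).

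How much of it can hold an attempt depends on g:

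| Gap g (days) | Exposed days, W = 89 to 92 |
|---|---|
| 0 | about 0 |
| 3 | 3 |
| 7 | 5 to 7 |
| 14 | 5 to 8 |

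At g = 0 the daily-smoking criterion covers the overhang, except for one day when W = 92 (8 − 7 = 1).

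**Survey late**

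| Days late | Pre-randomisation days in recall, W = 89 to 92 | Early days lost, W = 91 | Early days lost, W = 89 to 92 | Share of 84 days lost, W = 91 |
|---|---|---|---|---|
| 0 | 5 to 8 | 0 | 0 | 0% |
| 3 | 2 to 5 | 0 | 0 | 0% |
| 7 | 0 to 1 | 0 | 0 to 2 | 0% |
| 14 | 0 | 7 | 6 to 9 | 7/84 = 8.3% |
| 21 | 0 | 14 | 13 to 16 | 14/84 = 16.7% |
| 28 | 0 | 21 | 20 to 23 | 21/84 = 25.0% |

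A short delay therefore only shrinks the overhang. Loss of early follow-up begins once the survey is more than 5 to 8 days late, depending on W.

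**Can g exceed zero?** The documents leave room for it. Section 5.1 adds a baseline week. Section 6.1 allows unclear eligibility to go to the principal investigator, with an answer some days later. Section 12.0 lets people take time to decide before consenting. None of this fixes the length of the gap.

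**The case against.** The strongest reply is that the protocol treats 12 weeks and three months as one period. Section 4.0 describes a 12-week study and then monthly funds over three months. A participant who reads the item that way has no overhang, and recall over a quarter of a year may not resolve one week. This stands as a limit on size. It also shows that the intended period should be written down, since another participant may count calendar months.

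Second, the survey wording is not in the documents. Section 5.3 says it is attached to the ethics submission, and it may already name a date. This stands too. The endpoint definition in Section 3.0 still has no anchor.

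Third, the gap may be short. Section 5.2 has one call covering screening and consent, with the baseline survey after consent and no delay specified. The contact times in Section 5.1, leaving out the intervention-arm steps, sum to 140 to 180 minutes with the screening call and 110 to 150 without it. The stated total is 2.5 to 3 hours (150 to 180 minutes), which suggests that screening is counted within the 13 weeks. Exposure may therefore be near zero for many participants, but the documents neither require that nor rule out a week.

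Two stronger readings are tempting:
- A reader might spread first attempts evenly over the 30 days of the eligibility question. That would give 7/30 = 23% of first attempts before randomisation, and 23%, 47% and 70% (7/30, 14/30, 21/30) lost at two, three and four weeks late. The documents give no distribution of attempts. Cessation referrals begin only in Week 1 after randomisation, and the endpoints are the number of attempts and the longest abstinence, not first attempts.
- A reader might infer bias between arms because only one arm receives funds. Both arms have the same navigator calls and the same $35 follow-up payment, and nothing in the documents shows that survey timing differs by arm.

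**Conclusion.** The definition does not match the post-randomisation period, and it should be changed. Read as calendar months, an on-time recall runs 5 to 8 days past randomisation, and between about 0 and 8 of those days could hold an attempt that precedes allocation. This applies equally to both arms under 1:1 allocation, so it mainly adds noise or dilutes the difference. With a 91-day recall, surveys 14, 21 and 28 days late lose about 8%, 17% and 25% of the 84 days; a survey up to about a week late loses almost nothing.

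These figures assume calendar months, exact recall and no anchor in the unseen survey. The documents do not support saying that pre-randomisation attempts will be counted or that every late survey loses attempts. They show only that both can happen. Bias between arms remains conditional on lateness that differs by arm. The impact is modest: these are secondary endpoints in a 60-person pilot.

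**What to change.** 1. In Section 3.0, define both endpoints over the period from the date of randomisation to the date of the follow-up survey.
2. Have the follow-up survey display each participant's randomisation date, if it does not already.
3. State a completion window for the week-12 survey, say how later surveys are handled, and record the completion date.
4. Count only attempts and abstinent days on or after randomisation. For a run of abstinence already under way on that date, count only the days from then on.
5. Keep the three-month recall in the baseline survey as the baseline value.

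The recall then includes no pre-randomisation days and loses no early days, whatever the survey date. A strict cut-off at day 84 is not advised, because it would ask late responders to set aside recent attempts by date, which is harder to recall.

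The cost is a wording change in Section 3.0, a date field and possibly an added item in the survey, and a short rule on timing. The follow-up period no longer matches the baseline recall exactly (84 days against about 91). Its length also varies a little with the survey date: a survey 7 days late would cover 84 + 7 = 91 days. The completion window keeps that variation small.

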### 4.0 Study Intervention

Experimental procedures involve the provision of economic food assistance throughout the 12-week duration of the study. Participants in the intervention group will be provided with extra funds intended to provide short-term relief from food insecurity during the tobacco cessation attempt. Funds are distributed by either VISA gift cards, a check, direct deposit, or a Zelle transaction, based on the participant's choosing. This is done on a monthly basis for 3 months, at a maximum of \$250, divided across 3 months.

